## Study groups

This is a double-blind, individually-randomised trial with three study arms. For reference, the interventions given during the initial three-year trial are shown first, with the interventions given during the extension study shown separately.

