## **Study population in the original trial**

Children of either sex were eligible for inclusion in the trial, provided that they were 5-17 months of age on the scheduled date of first vaccination in April 2017, they were living permanently in the study area, and the consent of a parent or legally acceptable representative was obtained.

Children with a history of an adverse reaction to SP or AQ, known to have a serious underlying illness including known HIV infection not well controlled by treatment, having severe malnutrition (z scores < 3 SD) or known to have previously received a malaria vaccine were excluded from the trial.

Children known to have received SMC during the year prior to enrolment (either through the previous study in these districts (AZ-SMC, [NCT02211729](https://clinicaltrials.gov/ct2/show/NCT02211729)), or from the national programme) were not excluded from this study.

The list of eligible children in each country was sorted by location (village), age in months, gender and prior receipt of SMC, before assigning randomisation codes in permuted blocks of 9, to give an implicit stratification on these factors.

Children who were randomized but who did not receive the first dose of study vaccines in 2017 were deemed to have withdrawn consent and were not followed up further. Consequently, analyses from baseline of all the children who remained under observation constitute a modified ITT population, rather than the full ITT population. Analyses during specific years of the study, or during the extension study period only, reflect the children remaining in follow-up at that point, rather than analysis by intention to treat.

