### **Pre-specified Secondary analyses**

#### **Safety signals from the RTS,S/AS01 phase 3 studies**

The incidence of meningitis has been very low in the study cohort, with no events in the first three years of the trial. A 95% confidence interval for the incidence rate of meningitis among children vaccinated with RTS,S/AS01, over the whole intervention period, up to the age of five years, will be calculated.

The incidence of cerebral malaria among children vaccinated with RTS,S/AS01E will be investigated by comparing the RTS,S/AS01 groups with the SMC alone group, controlling for SMC status using an indicator variable. Cox regression will be used to obtain the hazard ratio and its 95% confidence interval over the whole intervention period, up to the age of five years.

The incidence of febrile convulsions not related to malaria or another obvious cause among children vaccinated with RTS,S/AS01 will be investigated as for cerebral malaria, i.e. by comparing the RTS,S groups with the SMC alone group, controlling for SMC status using an indicator variable. Cox regression will be used to obtain the hazard ratio and its 95% confidence interval over the whole intervention period, up to the age of five years. The excess cases per 1000 child-years at risk, based on the incidence rate differences will also be presented. The subset of febrile convulsions that occurred within 7 days of vaccination will also be analysed.

An exploratory analysis for data from the first three years of the trial found no evidence that RTS,S/AS01 increases mortality in girls. This will be repeated over the whole intervention period, up to the age of five years.

This was done by comparing the incidence of deaths using Cox regression, with an interaction between a dummy variable indicating receipt of RTS,S/AS01E and gender. The Wald test p-value for the interaction term will be used to assess evidence for effect modification. This model will also include a dummy variable for SMC to adjust for SMC receipt. This will enable the

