female: male mortality ratio and its 95% confidence interval to be calculated separately for RTS,S/AS01E recipients, and non-recipients. We will use indicator variables to obtain the ratio of these ratios, with the 95% confidence interval. We will also present the mortality ratio for RTS,S recipients versus non-recipients separately for males and females. Since it is hypothesised that this effect may be age-dependent, we will also carry out these analyses restricted to the period after the first booster dose.

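### The girls' mortality model assumes, without saying so, that SMC's effect on death is the same in girls and boys; per-arm sex ratios and Combined versus SMC alone by sex should be reported beside it

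*Combined protocol and SAP*

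**What the plan says.** The SAP, under Safety signals from the RTS,S/AS01 phase 3 studies, repeats over the whole intervention period a mortality analysis that it calls exploratory in its three-year form. The method is described as "comparing the incidence of deaths using Cox regression, with an interaction between a dummy variable indicating receipt of" RTS,S and gender. "The Wald test p-value for the interaction term will be used to assess evidence for effect modification". For SMC it adds one term: "This model will also include a dummy variable for SMC to adjust for SMC receipt".

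From this model the SAP wants the "female: male mortality ratio and its 95% confidence interval to be calculated separately" for RTS,S recipients and non-recipients, and then: "We will use indicator variables to obtain the ratio of these ratios, with the 95% confidence interval". It continues: "We will also present the mortality ratio for RTS,S recipients versus non-recipients separately for males and females". The same analyses are repeated for the period after the first booster.

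On design, the SAP says "This is a double-blind, individually-randomised trial with three study arms": SMC alone, RTS,S alone and Combined. It gives no allocation ratio in words, but codes were assigned to a sorted list, "before assigning randomisation codes in permuted blocks of 9", and Protocol section 10.2 plans 6875 person-years in each group, so 1:1:1 is assumed here.

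No other section adds an SMC-by-sex term for all-cause death. The Covariates section stratifies by country only. The sex interaction among the pre-specified subgroup analyses is for the primary outcome.

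**The concern.** Protocol section 7.2 lists an apparent rise in mortality among female vaccine recipients as one of the main phase 3 safety issues, and this is the analysis that addresses it. The comparison is between RTS,S recipients and non-recipients, and SMC is not balanced across it: non-recipients are all in the SMC-alone arm, while recipients are split between an arm with SMC and an arm without.

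An SMC main effect corrects for a difference in the level of mortality. It does not correct for a difference in the female:male ratio. If SMC shifts that ratio, the non-recipients carry the whole shift and the recipients about half, and the remainder appears as an RTS,S-by-sex effect. If SMC protects girls more than boys, the ratio of ratios moves up, towards an apparent excess in girls. If it protects them less, the ratio moves down. The contrast in which only RTS,S differs, Combined versus SMC alone by sex, is not planned for all-cause death.

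**Working it through.** The documents give no death count, power figure or SMC-by-sex figure for this analysis, so there is no stated result to reproduce. What follows is a sensitivity range.

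**Inputs.** From the documents: three arms, model terms as above, equal person-time per arm. Assumed: person-time split equally by sex, constant hazards, no RTS,S effect on death in boys, SMC mortality ratio s in boys (0.8 unless stated), SMC-by-sex ratio θ (girls' SMC mortality ratio divided by boys') between 0.5 and 2.0, and 60 or 120 total deaths.

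**Algebra.** Let c be the log female:male ratio without either intervention, d the true log RTS,S-by-sex ratio and e = ln θ. The log female:male ratios are:
- SMC alone: c + e
- RTS,S alone: c + d
- Combined: c + d + e

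The planned model fits one female:male ratio to both recipient arms, about c + d + e/2. Subtracting the non-recipients' c + e leaves about d − e/2.

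**Expected-count form.** With equal person-time, the fitted female:male ratio among recipients is total girls' deaths over total boys' deaths. With d = 0 this is (1 + sθ)/(1 + s), relative to the no-SMC ratio. Among non-recipients it is θ. The planned ratio of ratios is therefore

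(1 + sθ) / [(1 + s)θ], multiplied by exp(d) if d is not zero.

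With s = 0.8 and a true value of 1.00:

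| θ | SMC mortality ratio in girls (0.8θ) | (1 + 0.8θ)/(1.8θ) | Planned estimate |
|---|---|---|---|
| 0.5 | 0.40 | 1.40/0.90 | 1.56 |
| 0.67 | 0.54 | 1.536/1.206 | 1.27 |
| 0.8 | 0.64 | 1.64/1.44 | 1.14 |
| 1.0 | 0.80 | 1.80/1.80 | 1.00 |
| 1.25 | 1.00 | 2.00/2.25 | 0.89 |
| 1.5 | 1.20 | 2.20/2.70 | 0.81 |
| 2.0 | 1.60 | 2.60/3.60 | 0.72 |

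A log-linear fit of the stated model to the six arm-by-sex cells gives the same figures. A Cox fit to 120,000 simulated children (5,521 deaths, s = 1.0, θ = 1.5) gave 0.844 under the planned model, where the formula gives 2.5/3.0 = 0.833. With SMC-by-sex added it gave 1.015, against a true 1.00.

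The sex-specific RTS,S ratios from the same model also move. With s = 1.0 and θ = 1.5 they are 1.11 in boys and 0.93 in girls when both are truly 1.00.

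**Precision.** The planned variance is the sum of reciprocal deaths in four groups: girls and boys in SMC alone, and girls and boys in the two recipient arms together. With s = 0.8, θ = 1 and 120 deaths, the cells hold 120 × 0.8/5.2 = 18.46 per sex in SMC alone and in Combined, and 120 × 1/5.2 = 23.08 per sex in RTS,S alone.
- Planned: √(2/18.46 + 2/41.54) = 0.40. At 60 deaths, 0.40 × √2 = 0.56.
- With SMC-by-sex (Combined versus SMC alone only): √(4/18.46) = 0.47, which is 18% larger.

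Across s = 0.5 to 1.0 and θ = 0.5 to 2.0 the increase is 13-27%.

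**Bias against error.** At θ = 0.8 the bias is ln 1.14 = 0.13, about a third of a standard error at 120 deaths. At θ = 0.67 it is ln 1.27 = 0.24, about 0.6 of one.

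**The case against.** **The bias is conditional.** It needs SMC's effect on death to differ by sex, and nothing in the documents suggests that it does. The only sex modification they raise concerns RTS,S. Most interaction models omit some other interaction, and doing so can be a reasonable choice. This stands: the gap is an unstated assumption, not a demonstrated error.

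**A reader might infer that the model hides much of a real signal.** A true doubling would be estimated as 2 × 0.815 = 1.63 at θ = 1.5 and 2 × 0.722 = 1.44 at θ = 2.0. With s = 0.8, those values mean that SMC multiplies girls' mortality by 1.2 or 1.6. The protocol describes SMC as very safe, and the documents do not support that scenario. If SMC is neutral in girls (θ = 1.25), the estimate is 0.89 against 1.00.

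**A reader might infer that the test will often raise a false alarm.** The nominal 5% Wald test rejects in 5.5% to 14% of cases, over about 24 to 165 deaths, and that is with θ at 1.5 or 2.0. The point estimate is affected more than the p-value.

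**A reader might infer that the planned model should be replaced.** Root mean squared error on the log scale does not support that. At 120 deaths, planned versus with SMC-by-sex, it is 0.48 v 0.49 at θ = 0.67, 0.42 v 0.48 at 0.8, 0.41 v 0.46 at 1.25 and 0.44 v 0.46 at 1.5. At 60 deaths the planned model is better from 0.67 to 1.5. The added term wins at 120 deaths only at the extremes, though at 200 deaths it also wins at 0.67 and 1.5. It also makes the model saturated, so an excess of girls' deaths confined to the RTS,S-alone arm would be attributed to SMC-by-sex.

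**Part may already be covered.** The mortality ratios to be shown separately for males and females could come from sex-stratified fits, which would free the SMC effect. The SAP does not say, and the Wald test and ratio of ratios would remain as described. The subgroup section mentions malaria deaths just after its sex interaction. Even if that was meant to extend the interaction to them, it would not cover all-cause death.

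**Conclusion.** The point holds as a cheap improvement. The planned RTS,S-by-sex ratio of ratios is free of SMC-by-sex differences only if SMC's effect on death is equal in both sexes. The SAP should state that assumption, because the three-arm design gives it a direct route into the result. The leak is about minus half of any such difference on the log scale. With s = 0.8, that is 1.14 to 0.89 for SMC-by-sex ratios of 0.8 to 1.25, and 1.27 to 0.81 for 0.67 to 1.5, against a true 1.00.

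These figures rest on assumed SMC effects and equal person-time. The comparison with sampling error rests on assumed death counts. The documents do not show that the bias exists, that it would decide the conclusion, or that the planned analysis is wrong to lead.

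**What to change.** Keep the planned model and add a sentence saying that it takes SMC's effect on death as equal in girls and boys. Pre-specify alongside it, for the whole intervention period and for the period after the first booster:

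- deaths, person-time and the female:male mortality ratio in each of the three arms;
- the RTS,S-by-sex estimate, and the RTS,S mortality ratio in girls and in boys, from Combined versus SMC alone (equivalently, from the model with an SMC-by-sex term).

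Interpret any signal in girls in light of both estimates, and say whether the planned sex-specific ratios come from the joint model or from separate fits.

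The cost is one extra model and a few table rows, using data already held. The added estimate does not use the RTS,S-alone arm, which is why it belongs beside the planned one. The per-arm table keeps that arm's sex ratio in view. An RTS,S-by-SMC interaction remains inestimable, because no arm receives neither intervention.

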### **Ancillary analyses to be reported separately**

1. Analysis of the prevalence and frequency of molecular markers of resistance to SP and AQ in children with *P. falciparum* infection, among samples collected at the end of season cross-sectional survey in 2019, and at the final cross-sectional survey in December 2021. The molecular markers of interest include the dhfr 51-59-108 triple mutation, dhps-A437G, and dhps-K540E mutations for resistance to SP, and the pfcrt K76T and pfmdr1 N86Y mutations for resistance to AQ.
2. Secondary analyses are planned to investigate the association between malaria event history, and completeness of adherence to study interventions, with malaria incidence over time.
3. Regression approaches applied to data from the first three years of the trial will be applied to data from the final two years of the study, to obtain estimate the duration and profile of protection over time from the sixth and seventh doses of RTS,S/AS01E and SMC. Further secondary analyses will explore the changing relative benefits of SMC and RTS,S/AS01E with age and transmission intensity (by comparing efficacy profiles with age between Burkina Faso, which has higher incidence rates, with Mali).
4. Analyses of the primary vaccine effect, through stratification on event number, to account for potential differences in the acquisition of immunity in the different study groups over the course of the trial, and to determine whether any appearance of diminishing effectiveness of the interventions over time, could be explained by differences in acquired immunity in the single intervention groups compared to the combined group.
5. Analyses of rebound morbidity. The study cohort is being followed up beyond the observation period of the extension study, to determine whether prior randomisation group, adherence to the allocated interventions, and disease history is associated with morbidity post-intervention. While older children in the study cohort have been observed during their first year post-interventions (during the 2021 rainy season), it would be premature to draw conclusions about delayed morbidity post-intervention, as these older children who received their final (sixth) dose of RTS,S vaccine in June 2020 may continue to be partially protected from vaccination in 2021. For this reason, analyses to investigate morbidity in the post-intervention period will be reported separately after a longer period of follow-up.

### **Database and randomisation codes**

Data have been collected using electronic case record forms (eCRF) developed using Open Data Kit (ODK) software. Tablet PCs are used to document all intervention contacts and all active surveillance contacts such as the end of season cross-sectional surveys. For passive case detection, tablet PCs loaded with eCRFs are available at all study health centres that provide treatment. Data are transferred from the eCRFs held in the research sites to a central data management team. Automatic checks are performed on clinical and laboratory forms to ensure that they are complete and contain valid responses prior to transferring data. Further checking and cleaning of the data (including checks for duplicate entries, consistency and range checks of variables) is then carried out by the data management teams in Burkina Faso and Mali using MS Access.

The consistency of merges between different database tables will be undertaken blind to randomisation group. The analysis databases and analysis programmes (written as Stata do files) will also be prepared for the primary and key secondary analyses before the randomisation code is broken.

A final version of the database for analysis, following approval by the Data and Safety Monitoring Board (DSMB) will be archived on the LSHTM MyFiles system, and a copy sent to the chair of the DSMB for their records.

The study treatment group will only be released by the independent statistician when the final database is ready and authorisation is given by the DSMB.

All data used for analysis of the main trial report will be annotated and archived. Stata code used for the analyses will also be archived.

## Planned main tables for published report

**Dummy Table 1:** Incidence of the primary outcome until the end of the intervention period: number of cases of clinical malaria; person-years at risk (PYAR); rates per 1000 person-years; and P-values from tests of homogeneity among all study children. Results will also be shown by country with results of the test of interaction by country.

|                     | No. children | PYAR           | No. events  | Rate/1000
(95% CI)       | Rate Ratio
(95% CI) | Test of
homogeneity  | Interaction
by Country |
|---------------------|--------------|----------------|-------------|-----------------------------|------------------------|-------------------------------------|---------------------------|
| All children |              |                |             |                             |                        |                                     |                           |
| SMC                 | 2000         | 6000.0         | 1333        | 180.0 (120.0, 240.0)        | (Reference)            |                                     | P=0.0                     |
| RTS,S               | 2000         | 6000.0         | 1333        | 180.0 (120.0, 240.0)        | 1.00 (0.90, 1.10)      | Reference                           |                           |
| Combined            | 2000         | 6000.0         | 1333        | 180.0 (120.0, 240.0)        | 1.00 (0.90, 1.10)      | 1.00 (0.90, 1.10)                   |                           |
| Total        | 6000  | 18000.0 | 4000 | 180.0 (120.0, 240.0) | -                      | -                                   | -                         |
| Burkina Faso |              |                |             |                             |                        |                                     |                           |
| SMC                 | 2000         | 6000.0         | 1333        | 180.0 (120.0, 240.0)        | (Reference)            |                                     | P=0.0                     |
| RTS,S               | 2000         | 6000.0         | 1333        | 180.0 (120.0, 240.0)        | 1.00 (0.90, 1.10)      | Reference                           |                           |
| Combined            | 2000         | 6000.0         | 1333        | 180.0 (120.0, 240.0)        | 1.00 (0.90, 1.10)      | 1.00 (0.90, 1.10)                   |                           |
| Total        | 6000  | 18000.0 | 4000 | 180.0 (120.0, 240.0) | -                      | -                                   | -                         |
| Mali         |              |                |             |                             |                        |                                     |                           |
| SMC                 | 2000         | 6000.0         | 1333        | 180.0 (120.0, 240.0)        | (Reference)            |                                     | P=0.0                     |
| RTS,S               | 2000         | 6000.0         | 1333        | 180.0 (120.0, 240.0)        | 1.00 (0.90, 1.10)      | Reference                           |                           |
| Combined            | 2000         | 6000.0         | 1333        | 180.0 (120.0, 240.0)        | 1.00 (0.90, 1.10)      | 1.00 (0.90, 1.10)                   |                           |
| Total        | 6000  | 18000.0 | 4000 | 180.0 (120.0, 240.0) | -                      | -                                   | -                         |

Numbers are included only to give an idea of layout / spacing.

**Dummy Table 2:** Incidence of the primary outcome by study year: number of cases of clinical malaria; person-years at risk (PYAR); rates per 1000 person-years; and P-values from tests of homogeneity among all study children. The results of the test of interaction by study year will also be shown.

|                     | No. children | PYAR          | No. events  | Rate/1000 (95% CI)          | Rate Ratio (95% CI) | Test of homogeneity  | Interaction by Year |
|---------------------|--------------|---------------|-------------|-----------------------------|---------------------|----------------------------------|---------------------|
| Study Year 4 |              |               |             |                             |                     |                                  |                     |
| SMC                 | 2000         | 2000.0        | 1333        | 180.0 (120.0, 240.0)        | (Reference)         |                                  | P=0.0               |
| RTS,S               | 2000         | 2000.0        | 1333        | 180.0 (120.0, 240.0)        | 1.00 (0.90, 1.10)   | Reference                        |                     |
| Combined            | 2000         | 2000.0        | 1333        | 180.0 (120.0, 240.0)        | 1.00 (0.90, 1.10)   | 1.00 (0.90, 1.10)                |                     |
| Total        | 6000  | 6000.0 | 4000 | 180.0 (120.0, 240.0) | -                   | -                                | -                   |
| Study Year 5 |              |               |             |                             |                     |                                  |                     |
| SMC                 | 1000         | 1000.0        | 1333        | 180.0 (120.0, 240.0)        | (Reference)         |                                  | P=0.0               |
| RTS,S               | 1000         | 1000.0        | 1333        | 180.0 (120.0, 240.0)        | 1.00 (0.90, 1.10)   | Reference                        |                     |
| Combined            | 1000         | 1000.0        | 1333        | 180.0 (120.0, 240.0)        | 1.00 (0.90, 1.10)   | 1.00 (0.90, 1.10)                |                     |
| Total        | 3000  | 3000.0 | 4000 | 180.0 (120.0, 240.0) | -                   | -                                | -                   |

Numbers are included only to give an idea of layout / spacing.

Similar tables will be used to report the incidence of passively detected secondary outcomes.

[figure not shown]
**Dummy Table 3:** Prevalence of *P. falciparum* infection at the end of malaria transmission season surveys: number of children tested; number with the outcome of interest; prevalence (95% CI); prevalence ratio (95% CI) and P-values from tests of homogeneity will be shown.

|                                       | No. children with result | No. with outcome | Prevalence (95% CI)      | Prevalence Ratios (95% CI) | Test of homogeneity  |
|---------------------------------------|--------------------------|------------------|--------------------------|----------------------------|----------------------------------|
| P. falciparum infection |                          |                  |                          |                            |                                  |
| All study children – 2020      |                          |                  |                          |                            |                                  |
| SMC                                   | 2000                     | 200              | 10.0 (5.00, 15.0)        | (Reference)                | P=0.0                            |
| RTS,S                                 | 2000                     | 200              | 10.0 (5.00, 15.0)        | 1.00 (0.90, 1.10)          | Reference                        |
| Combined                              | 2000                     | 200              | 10.0 (5.00, 15.0)        | 1.00 (0.90, 1.10)          | 1.00 (0.90, 1.10)                |
| Total                          | 6000              | 600       | 10.0 (5.00, 15.0) | -                          | -                                |
| All study children – 2021      |                          |                  |                          |                            |                                  |
| SMC                                   | 2000                     | 200              | 10.0 (5.00, 15.0)        | (Reference)                | P=0.0                            |
| RTS,S                                 | 2000                     | 200              | 10.0 (5.00, 15.0)        | 1.00 (0.90, 1.10)          | Reference                        |
| Combined                              | 2000                     | 200              | 10.0 (5.00, 15.0)        | 1.00 (0.90, 1.10)          | 1.00 (0.90, 1.10)                |
| Total                          | 6000              | 600       | 10.0 (5.00, 15.0) | -                          | -                                |

Numbers are included only to give an idea of layout / spacing.

Similar tables will be used to report the prevalence of other secondary outcomes measured at the end of transmission season surveys, and weekly surveys.

[figure not shown]
**Dummy Figure 1.** This will show i) cumulative hazards of malaria, by treatment group and ii) the risk of malaria, by treatment group. As an example, the plot from the first 3 years of the trial is shown.

